9 ETHICS

9.1 Institutional Review Board (IRB)/Ethics Committee (EC)

It is the responsibility of the investigator to have prospective approval of the study protocol, protocol amendments, ICFs, and other relevant documents, e.g., written participant instructions, recruitment advertisements, if applicable, from the IRB/EC before participation of human participants in research studies. All correspondence with the IRB/EC should be retained in the Investigator Site File. Copies of IRB/EC approvals should be forwarded to the sponsor.

All IRB/EC approvals should be signed by the IRB/EC chairperson or designee and must identify the IRB/EC name and address, the clinical protocol by title or protocol number or both, and the date approval or a favorable opinion was granted.

The Investigator is responsible for providing written summaries of the progress and status of the study at intervals not exceeding 1 year or otherwise specified by the IRB/EC. The Investigator must promptly supply the sponsor or its designee, the IRB/EC, and, where applicable, the institution, with written reports on any changes significantly affecting the conduct of the study or increasing the risk to participants.

9.2 Ethical Conduct of the Study

The study will be performed in accordance with the ethical principles that have their origin in the Declaration of Helsinki and all applicable regulations. In addition, the study will be conducted in accordance with the protocol, the International Conference on Harmonisation (ICH) tripartite guideline E6 (R2), Good Clinical Practice (GCP), and applicable local regulatory requirements and laws.

9.3 Participant Information and Consent

Written informed consents that meet the requirements of 21 Code of Federal Regulations (CFR) 50, local regulations, ICH guidelines, privacy and data protection laws applicable in the respective participating countries and the IRB/IEC or study center shall be obtained from each participant before entering the study, upon re-screening, and when performing any unusual or non-routine procedure that involves risk to the participant. Informed consent templates may be provided by the sponsor to investigative sites. If any institution-specific modifications to study-related procedures are proposed or made by the site, the consents should be reviewed by the sponsor or its designee or both before IRB/EC submission. Once reviewed, the consents will be submitted by the Investigator to his or her IRB/EC for review and approval before the start of the study. If the ICF is revised during the course of the study, all active participating participants must sign the revised form.

Before recruitment and enrollment, each prospective participant or his or her legal guardian will be given a full explanation of the study and be allowed to read the approved ICF. Once the Investigator is assured that the participant/legal guardian understands the implications of participating in the study, the participant/legal guardian will be asked to give consent to participate in the study by signing the ICF. Participants will be made aware that they may

withdraw from the study at any time for any reason.

The Investigator shall retain the signed original ICF(s) and give a copy of the signed original form to the participant or legal guardian.

10 INVESTIGATOR'S OBLIGATIONS AND STUDY PERSONNEL

The study will be conducted by qualified investigators under the sponsorship of Palladio Biosciences, Inc. (the sponsor).

The contact information for the sponsor's Chief Medical Officer, the CRO's medical monitor, other sponsor and CRO personnel (Premier Research is the designated CRO), and other study vendors are listed in the Investigator Site File provided to each site.

The following administrative items are meant to guide the Investigator in the conduct of the study but may be subject to change based on industry and government standard operating procedures, working practice documents, or guidelines. Changes will be reported to the IRB but will not result in protocol amendments.

10.1 Confidentiality

All laboratory specimens, evaluation forms, reports, and other records will be identified in a manner designed to maintain participants' confidentiality. All records will be kept in a secure storage area with limited access. Clinical information will not be released without participants' (or legal guardians') written permission, except as necessary for monitoring and auditing by the sponsor, its designees, the US Food and Drug Administration (FDA), European Medicines Agency (EMA) or other health or regulatory authority or the IRB/EC.

The Investigator and all employees and coworkers involved with this study may not disclose or use for any purpose other than performance of the study any data, record, or other unpublished, confidential information disclosed to those individuals for the purpose of the study. Prior written agreement from the sponsor or its designee must be obtained for the disclosure of any said confidential information to other parties.

10.2 Financial Disclosure and Obligations

Investigators and sub-investigators will provide the sponsor with sufficient, accurate financial information as requested to allow the sponsor to submit complete and accurate financial certification or disclosure statements to the appropriate regulatory authorities. In addition, Investigators and sub-investigators must provide to the sponsor a commitment to promptly update this information if any relevant changes occur during the course of the investigation and for 1 year following the completion of the study.

Neither the sponsor nor sponsor's representatives are financially responsible for further testing or treatment of any medical condition that may be detected during the screening process. In addition, in the absence of specific arrangements, neither the sponsor nor sponsor's representatives are financially responsible for further treatment of the participant's disease.

10.3 Investigator Documentation

Before beginning the study, the Investigator will be asked to comply with ICH E6 (R2) [Section 10.4](#) and Title 21 of the CFR by providing the following essential documents, including but not limited to:

- IRB/EC written approval and any other local approval, as appropriate
- Original signed Investigator agreement page of the protocol
- Form FDA 1572, fully executed (where applicable), and all updates on a new fully executed Form FDA 1572
- Curriculum vitae for the Investigator and each Sub-Investigator
- Financial disclosure information to allow the sponsor to submit complete and accurate certification or disclosure statements to the appropriate regulatory authorities. In addition, the Investigators must provide to the sponsor a commitment to promptly update this information if any relevant changes occur during the course of the investigation and for 1 year after the completion of the study.
- IRB/EC-approved informed consent, samples of site advertisements for recruitment for this study, and any other written information regarding this study that is to be provided to the participant or legal guardian, and
- Laboratory certifications and normal ranges for any local laboratories used by the site.

10.4 Study Conduct

The Investigator agrees that the study will be conducted according to the principles of ICH E6 (R2). The Investigator will conduct all aspects of this study in accordance with all national, state, and local laws or regulations. Study information from this protocol will be posted on publicly available clinical trial registers before enrollment of participants begins.

10.5 Adherence to Protocol

The Investigator agrees to conduct the study as outlined in this protocol in accordance with ICH E6 (R2) and all applicable guidelines and regulations.

10.6 Adverse Events and Study Report Requirements

By participating in this study, the Investigator agrees to submit reports of SAEs according to the timeline and method outlined in the protocol. In addition, the Investigator agrees to submit annual reports to the study site IRB/EC as appropriate.

10.7 Investigator's Final Report

Upon completion of the study, the Investigator, where applicable, should inform the institution; the Investigator/institution should provide the IRB/EC with a summary of the study's outcome and the sponsor and regulatory authority with any reports required.

10.8 Records Retention

To enable evaluations and/or audits from regulatory authorities or the sponsor, the investigator agrees to keep records, including the identity of all participating participants

(sufficient information to link records, e.g., eCRFs and hospital records), all original signed ICFs, copies of all eCRFs, SAE forms, source documents, and detailed records of treatment disposition, and adequate documentation of relevant correspondence (e.g., letters, meeting minutes, telephone calls reports). The records should be retained by the investigator according to ICH, local regulations, or as specified in the Clinical Study Agreement, whichever is longer.

If the investigator becomes unable for any reason to continue to retain study records for the required period (e.g., retirement, relocation), the sponsor should be prospectively notified. The study records must be transferred to a designee acceptable to the sponsor, such as another investigator, another institution, or to the sponsor. The investigator must obtain the sponsor's written permission before disposing of any records, even if retention requirements have been met.

Essential documents should be retained until at least 2 years after the last approval of a marketing application in an ICH region and until there are no pending or contemplated marketing applications in an ICH region, or at least 2 years have elapsed since the formal discontinuation of clinical development of the study drug. These documents should be retained for a longer period, however, if required by the applicable regulatory requirements or by an agreement with the sponsor. It is the responsibility of the sponsor to inform the Investigator/institution as to when these documents no longer need to be retained.

10.9 Publications

After completion of the study, the data may be considered for reporting at a scientific meeting or for publication in a scientific journal. In these cases, the study steering committee will be responsible for these activities and will work with the Investigators to determine how the manuscript is written and edited, the number and order of authors, the publication to which it will be submitted, and other related issues. The steering committee has final approval authority over all such issues.

Data are the property of the sponsor, but data and publication thereof will not be unduly withheld.

11 STUDY MANAGEMENT

11.1 Monitoring

11.1.1 Monitoring of the Study

The Clinical Research Associate (CRA) and/or designee, as a representative of the sponsor, has the obligation to follow the study closely. In doing so, the CRA will visit the Investigator and study site at periodic intervals, or conduct central or remote monitoring, in addition to maintaining necessary telephone, email and letter contact. The CRA will maintain current personal knowledge of the study through observation, review of study records and source documentation, and discussion of the conduct of the study with the Investigator and personnel.

All aspects of the study will be carefully monitored, by the sponsor or its designee, for compliance with applicable government regulation with respect to current GCP and current standard operating procedures.

11.1.2 Inspection of Records and Quality Assurance

Investigators and institutions involved in the study will permit study-related monitoring, audits, IRB/EC review, and regulatory inspections by providing direct access to all study records. In the event of an audit or inspection, the Investigator agrees to allow the sponsor, representatives of the sponsor, or a regulatory agency (e.g., FDA, EMA or other regulatory agency) access to all study records.

It is important that the investigator(s) and their relevant personnel are available during the monitoring visits and possible audits or inspections and that sufficient time is devoted to the process.

The Investigator should promptly notify the sponsor and/or its designee of any inspections scheduled by any regulatory authorities and promptly forward copies of any related reports received to the sponsor.

11.2 Management of Protocol Amendments and Deviations

11.2.1 Modification of the Protocol

Any changes in this research activity, except those necessary to remove an apparent, immediate hazard to the participant, must be reviewed and approved by the sponsor or its designee. Amendments to the protocol must be submitted in writing to the Investigator's IRB/EC for approval before participants can be enrolled into an amended protocol, and before the changes can be implemented.

11.3 Protocol Deviations

The Investigator or designee must document and explain in the participant's source documentation any deviation from the approved protocol. The Investigator may implement a deviation from, or a change of, the protocol to eliminate an immediate hazard to study participants without prior IRB/EC approval. As soon as possible after such an occurrence,

the implemented deviation or change, the reasons for it, and any proposed protocol amendments should be submitted to the IRB/EC for review and approval, to the sponsor for agreement, and to the regulatory authorities, if required.

A protocol deviation is defined as an unintended or unanticipated departure from the procedures or processes approved by the sponsor and the IRB and agreed to by the Investigator. A major deviation occurs when there is not adherence to the protocol by the participant or Investigator that results in a significant, additional risk to the participant. Major deviations can include not adhering to inclusion or exclusion criteria or not adhering to FDA regulations or ICH GCP guidelines, and will lead to the participant being withdrawn from the study (Section 4.2.5).

Protocol deviations will be documented by the Clinical Monitor throughout the course of monitoring visits. Investigators will be notified in writing by the monitor of deviations. The IRB/EC should be notified of all protocol deviations in a timely manner.

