4.2.5 Reasons for Treatment/Study Discontinuation

Participants who permanently discontinue study treatment before the end of the study, should be encouraged to continue in the study through the last study visit. They may discontinue or may be discontinued from study drug or from the study for any of the following reasons.

Note: Participants who discontinue from the study following randomization are not eligible to re-enroll.

1. Noncompliance with the protocol (protocol deviation);
2. Noncompliance with study drug;
3. Lack of efficacy (including need for transplantation or dialysis);
4. A serious or intolerable AE that, in the Investigator's opinion, requires discontinuation of study drug or permanent withdrawal from the study, including but not limited to laboratory safety assessments that reveal clinically significant (CS) hematological or biochemical changes from the baseline values, other than changes that are expected for vasopressin antagonists, and symptoms or an intercurrent illness that justifies withdrawal. Mild elevations in serum creatinine or serum sodium are known pharmacodynamic effects of vasopressin antagonists like lixivaptan and are transient and reversible. Therefore, participants should not be withdrawn due to mildly elevated serum creatinine or serum sodium and should be discussed with the medical monitor, if necessary;
5. Death;
6. Lost to follow-up (detailed procedures to prevent such loss are discussed further);
7. Withdrawal of consent (partial or complete);
8. Investigator or sponsor decides to discontinue the participant's participation in the study;
9. Pregnancy;
10. Site terminated by sponsor;
11. Study terminated by sponsor;
12. Other (e.g., trial burden, development of contraindication to use of study drug).

Upon occurrence of an SAE or intolerable AE, the Investigator will confer with the medical monitor and sponsor. If a participant is discontinued from study drug because of an AE, the event will be followed until it is resolved or stable as determined by the Investigator.

Additionally, the procedures described in [Section 4.2.4](#) (Treatment Discontinuation) should be followed. Any participant may withdraw his or her consent at any time. Participants' safety will be closely monitored throughout the study, and the study will be conducted following Good Clinical Practices (GCP).

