4.2.8 Withdrawal of Consent

Participants are free to withdraw from the study or study drug at any time. Participation in the study may be stopped at any time at the discretion of the Investigator or at the request of the sponsor. Participants should be followed for all protocol-specified evaluations and assessments, even after premature discontinuation of study drug, unless there is written withdrawal of consent or other written documentation by the Investigator confirming the participants' verbal intent to completely withdraw from the trial. Declining follow up by all of the methods listed below will constitute a withdrawal of consent (these methods of follow up will also be noted in the trial ICF).

- Participation in all study visits and/or procedures specified in the protocol (whether in-clinic, by telephone, or by an in-home visit).
- Participation in a subset of protocol-specified visits and/or procedures (by a frequency schedule and method as agreed by participant and Investigator).
- Contact of the participant by trial personnel, even if only by telephone, to assess current medical condition and obtain necessary medical or laboratory reports relevant to the trial's objectives.
- Access to medical information from alternative sources (e.g., hospital/clinic medical records, referring doctor's notes, public records, dialysis, transplantation or vital registries, social media sources).

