6.9 Early Termination Procedures

Participants who terminate from the study during Screening will not have follow up assessments.

Participants who terminate from the study during Part 1 at any time after the start of the Placebo Run-in Period will undergo Visit 22/ET procedures within 7 days of the last dose of study drug. Randomized participants will additionally complete Follow-up Period I for final assessments of safety and efficacy. Participants who terminate from the study at any time during Part 2 will undergo Visit 42/ET procedures within 7 days of the last dose of study

drug and additionally complete Follow-up Period II for final assessments of safety and efficacy.

Note: the intent of this study is that all randomized participants complete all visits and procedures regardless of whether study drug is continued or not. Detailed information about accommodating participants who may not be able or want to continue in the study is available as follows:

- Treatment Discontinuation – [Section 4.2.4](#)
- Methods to Prevent Loss to Follow Up – [Section 4.2.7](#)
- Withdrawal of Consent – [Section 4.2.8](#)
- Minimization of Missing Data: Study and Study Treatment Modification – Appendix 5 ([Section 13.5](#))

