6.1.4. Handling of Dropouts or Missing Data

Assessments are planned, by protocol, to be collected from all randomized participants except those who 1) withdraw consent AND 2) do not consent to any collection of data. Every effort will be made to keep randomized participants in the study and offer them options for continued treatment and, at a minimum, continued study participation to the degree possible; strategies of these efforts are described in the study protocol Section 4.2.4, Section 4.2.7, and Appendix 5 (Section 13.5) in order to minimize missing data. While all possible efforts will be made to ensure that participants stay in the study and all data is collected as scheduled, the occurrence of missing data cannot be completely eliminated.

The handling of missing data is dependent upon the efficacy analyses (see Section 8 Efficacy Analysis for detail). The missing data for efficacy analyses are generally imputed by the following methods:

• Missing at random (MAR) – mixed-effects model for repeated measures (MMRM): a modeling approach (missing data are not imputed prior to the analysis)

- Missing at random (MAR) multiple imputation (MI)
- Missing not at random (MNAR) multiple imputation (MI) with assumptions of missing not at random. Treatment impact on efficacy endpoints for missing data varies independently on the two treatment arms bi-dimensionally. Pattern-mixture approach is applied to investigate the MNAR pattern based on dropout reasons. Specifically, MNAR in the following patterns of dropout reasons will be investigated as MNAR:
 - Lack of efficacy (LOE)
 - LOE and adverse events (AE)
 - All dropouts

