- Prohibited Medications Use of a prohibited concomitant medication
- Dosing Adherence defined as taking less than 80% of the protocol-specified amount of study drug across the study

- Randomization error
- Mis-stratification of a participant within IRT system
- Drug dispensation without IRT assignment, incorrect drug kit administration, dose mistakes over inappropriate titration/re-titration
- Used the study drug with incorrect storage (temperature excursions, improper transport, security, etc.) which compromises Investigational Product safety or chemical activity
- MRI examination of kidneys during the screening, in Follow Up Period I, in Follow Up Period II not done/done with deviation from imaging technique described in Imaging manual
- Serum creatinine blood sample from Screening, Placebo Run-In, Follow-up Period I (or for participants who discontinue treatment prior to Visit 22, from the Follow-up Period following study drug treatment discontinuation) and Follow-up Period II not collected/ not sent to Central Lab for evaluation/ non evaluable, laboratory manual requirements not followed, serum creatinine result missing for any other reason, age/ sex/ race data missing or incomplete
- Liver Chemistry laboratory sample not collected/ not performed as required per protocol
- Repeat Liver Chemistry tests not performed within 48 hours of knowledge that aminotransferase levels >3 x ULN or total bilirubin >2 x ULN

The following deviation codes will be used to categorize/summarize the important protocol deviation above:

- Inclusion Criteria
- Exclusion Criteria
- Study Drug
- Assessment Safety
- Assessment Efficacy
- Lab Endpoint Data
- Visit Window
- Informed Consent
- Prohibited Medication
- Other

Study participants will be excluded from the PPAS if they meet any of the following criteria:

- Participant who did not meet all inclusion and exclusion criteria
- Placebo randomized participant who received lixivaptan treatment

- Lixivaptan randomized subject who received placebo treatment only throughout study
- Any participant who received protocol prohibited medications that could affect efficacy
- Participant with overall study treatment compliance of less than 80%

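### Protocol 11.3 orders withdrawal from the study after a major deviation, against the rule elsewhere that randomised participants stay in follow-up; the avoidable loss is mainly Week 52, on-treatment and Part 2 data

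*Protocol*

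**What the plan says.** Protocol 11.3 defines a major deviation as non-adherence that "results in a significant, additional risk to the participant". It adds that "Major deviations can include not adhering to inclusion or exclusion criteria", or breaches of FDA regulations or GCP, and that such deviations "will lead to the participant being withdrawn from the study". It then points to 4.2.5.

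Other sections take a different line:

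- Protocol 4.2.5, the section cited, is permissive: "They may discontinue or may be discontinued from study drug or from the study for any of the following reasons". Protocol deviation is the first reason listed. The section opens by encouraging people who stop drug to continue to the last visit.
- Protocol 4.2.8: "Participants should be followed for all protocol-specified evaluations and assessments, even after premature discontinuation of study drug". The exception is documented, complete withdrawal of consent.
- Protocol 6.9: "the intent of this study is that all randomized participants complete all visits and procedures regardless of whether study drug is continued or not".
- SAP 6.1.4: "Assessments are planned, by protocol, to be collected from all randomized participants except those who 1) withdraw consent" and who also refuse any further data collection. A major deviation is not an exception.
- SAP 7.2 lists "Participant who did not meet all inclusion and exclusion criteria" among the grounds for leaving the per-protocol set. The other analysis sets in SAP section 5 carry no such exclusion.
- Protocol 3.1.2 keeps participants whose baseline eGFR falls outside the entry range once recalculated with the 2021 equation.

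**The concern.** The 11.3 wording is mandatory and takes the participant out of the study, not merely off study drug. A site that finds an eligibility or GCP breach after randomisation is told by 11.3 to end participation, and by 4.2.8, 6.9 and the SAP to go on collecting data. Where 11.3 is followed, observations the plan intends to use are lost for an administrative reason. The loss is permanent: 4.2.5 bars re-enrolment after randomisation and 4.2.9 rules out replacement.

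The analysis most exposed is the one meant to test robustness to missing data. Protocol 8.4.2 bases the main sensitivity analysis on off-treatment eGFR after Week 52 for everyone randomised, whatever their adherence. SAP 8.2.1.1 specifies a version of it on the modified intent-to-treat set. Values that could have been observed would be imputed instead.

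**Working it through.** **1. What happens to a randomised participant withdrawn in Part 1.** Take, for illustration, withdrawal with the last dose at Week 12.

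- *Primary eGFR.* Protocol 6.9 requires the early-termination visit and then Follow-up Period I for randomised participants who terminate from the study. Table 3 footnote f says the same for those who stop drug or withdraw. For early stoppers the primary endpoint (Protocol 2.2.1.1, SAP 4.1.1.1) uses eGFR taken 8 to 28 days after the last dose, and the primary efficacy set needs only one such value. The primary value therefore survives unless the site reads 11.3 as ending all contact.
- *Week 52 off-treatment eGFR.* Protocol 4.2.4 asks participants who stop drug to stay for all remaining visits, which would supply this value. Withdrawal from the study removes it.
- *On-treatment eGFR after Week 12.* This is lost to the slope analysis (SAP 8.3.1). The loss is attributable to 11.3 only if study drug would otherwise have continued, since the endpoint uses on-treatment values alone.
- *Part 2.* All Part 2 data are lost.

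**2. How much noisier the primary value becomes.** The annualising factor is 365.25 divided by the days from the median baseline date to the median follow-up date. The nominal schedule in Protocol Table 3 gives:

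- Median baseline date: Visit 2. Run-in of 1 week plus titration of 5 to 6 weeks puts randomisation 6 to 7 weeks later.
- Median follow-up date: Visit 24, between day 9 and day 27 after the last dose (Visit 23 at day 8, Visit 25 at day 28, at least 24 hours from each).
- Last dose at Week 12: 18 to 19 weeks is 126 to 133 days; adding 9 to 27 gives 135 to 160 days. Factor: 365.25/135 = 2.71 to 365.25/160 = 2.28.
- Last dose at Week 52: 58 to 59 weeks is 406 to 413 days; adding 9 to 27 gives 415 to 440 days. Factor: 365.25/415 = 0.88 to 365.25/440 = 0.83.

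Measurement error in the observed change is therefore multiplied by about 2.3 to 2.7 rather than 0.83 to 0.88, roughly three times as much. SAP 8.2 recognises the problem: it caps early stoppers' annualised changes at the range seen in on-treatment completers.

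**3. The sample-size allowance.** Inputs from Protocol 8.1: difference 1.40, SD 6.20, alpha 0.01, power 90%, allocation 2:1. Sidedness is not stated for the primary test; two-sided is assumed.

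- Placebo n = (1 + 1/2) × (2.576 + 1.282)² × (6.20/1.40)² ≈ 437.7, rounded up to 438. Lixivaptan 876, total 1314. This matches the plan; a one-sided test would give 1149.
- Allowance for losses of every kind: 1350 − 1314 = 36, or 36/1350 = 2.67%.
- Power by share of participants with no primary value, from any cause (shares are assumptions): 0%, 90.9%; 2%, 90.3%; 2.67%, 90.0%; 5%, 89.2%; 10%, 87.2%.

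These figures describe total loss of primary values. None of it can be assigned to 11.3, because the documents give no rate of major deviations and step 1 shows that a withdrawn participant normally still has a primary value.

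**The case against.** The strongest reply is that the operative sections already contain the damage. Sections 6.9 and footnote f secure the follow-up eGFR. Major deviations are limited to those adding significant risk. The section 11.3 cites is permissive. Section 4.2.4 encourages continued attendance rather than guaranteeing it, and 6.9 states an intent. Missing Week 52 values are to be handled by multiple imputation, with tipping-point analyses also specified. On this view 11.3 is loose boilerplate.

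Much of that stands, and it rules out three stronger readings a reader might draw:

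- *That 11.3 in itself makes primary data missing.* It does so only if a site disregards 6.9 and footnote f.
- *That withdrawal would select differently by arm through tolerability or compliance.* Eligibility status is fixed before randomisation. Compliance below 80% leads to a recorded deviation and re-education (Protocol 5.4), and dose reduction or interruption for tolerability is permitted (4.2.3, 5.2). A difference between arms is not shown.
- *That the loss can be set against the 36-participant allowance.* An assumed 2% to 5% of 1350 would be 27 to 68 people, but the rate is not in the documents and the comparison counts each withdrawal as a lost primary value.

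What does not stand is the suggestion that nothing is lost. Imputation mitigates a missing Week 52 value but does not replace an observation that could have been made, and footnote f protects neither Week 52 nor Part 2.

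The reply is also right that an unconditional instruction to keep everyone for every assessment would go too far. Consent may not have been validly obtained (an important deviation in SAP 7.2), or the breach may be an MRI contraindication.

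**Conclusion.** The contradiction is real and should be corrected. Section 11.3 mandates leaving the study; 4.2.5 merely allows it; 4.2.8, 6.9 and SAP 6.1.4 point to continued follow-up; and SAP 7.2 treats an eligibility failure as a per-protocol matter. Where 11.3 is followed alongside 6.9, the losses are the Week 52 off-treatment eGFR, on-treatment eGFR that would otherwise have accrued, and Part 2 data, plus an annualised primary value with about three times the scaling of a completer's in the Week 12 illustration. Loss of the primary value itself is a risk under a literal reading of 11.3, not an expected result.

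The size cannot be computed without a major-deviation rate. Even if 5% of primary values were lost from all causes, power would be 89.2%, so the case rests on avoidable missing data rather than power. SAP section 12 reports five participants randomised before early termination and no statistical analyses, so the results of this trial are unaffected; the defect is in the text of the plan.

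**What to change.** Reconcile 11.3 with 4.2.5, 4.2.8 and 6.9 by separating decisions about study drug from follow-up in the study. In place of the withdrawal clause, state that:

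- major deviations are documented and reviewed;
- randomised participants remain in follow-up, at minimum for Follow-up Period I and the Week 52 off-treatment eGFR;
- the exceptions are consent that is withdrawn or was not validly obtained, and any single assessment that is unsafe for that participant;
- the deviation is handled in analysis through the per-protocol set, as SAP 7.2 already does for eligibility failures.

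Whether study drug continues is a separate clinical decision and is not addressed here. The cost is a short edit in a protocol amendment. No SAP analysis has to change.

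The reasons for leaving the study in 4.2.5, such as an investigator or sponsor decision, should be read against the new wording so that the two sections do not conflict again.
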